9.4 Procedures for Accounting for Missing, Unused, and Spurious Data

Subjects who do not comply with the requirements of this study will be dropped. Any subject who withdraws from this study or is dropped for cause may be replaced to ensure that a minimum of 20 subjects complete the study. In the event that lost subjects have a material effect on the analysis of the study and the importance of the conclusions drawn from the study, efforts will be made to consult with the study requester and a statistician to discuss how to best address the issues.

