4.6.2 Subject Discontinuation

The Investigator may discontinue individual subjects from the study at any time. Subjects may voluntarily withdraw from the study at any time. The Investigator will provide a written report on the appropriate CRF describing the reason for discontinuance and the date of discontinuance.

A subject who discontinues may be replaced with another qualified subject who will follow the same treatment scheme as the discontinued subject in order to finish with a minimum of 20 subjects.

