4.9.2 Protocol Deviations

A deviation is a departure from the protocol.

A protocol deviation is only for an individual subject. Protocol deviations are documented on a Protocol Deviation CRF.

Deviations that potentially affect 1) subject safety, rights or welfare, 2) data integrity or 3) compromise the statistical analysis of the study require immediate communication to 3M; the Investigator must contact the 3M study monitor within 24 hours of occurrence [contact]). A Protocol Deviation Form must be completed by the Investigator and include the type of deviation and a description of the circumstances surrounding the deviation.

Deviations which are made to protect the life or physical well-being of a subject in an emergency must be reported to the IRB within 24 hours after the Investigator learns of the occurrence.

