5.0 Subject Selection

5.1 Subject Inclusion Criteria

Subjects will be infants or children of either gender who meet the following criteria:

1. Who are healthy and who have intact skin at the test site with a baseline score of 0 for erythema
2. Who are between the ages of 6 months – 4 years of age (48 months)
3. Who have a Fitzpatrick Skin Type of I, II or III
4. Whose parent or legal representative agrees to not use any products (i.e. topical medications, creams, powders or ointments) on the test sites for 24 hours prior to the study start date
5. Whose parent or legal representative agrees to sponge bathe their child during the study but agrees to not bathe their child 1 hour before each visit.
6. Whose parent or legal representative agrees to not soak the tape during a sponge bath. If the site gets wet, parent or legal representative agrees to pat their child's back dry (no rubbing).
7. Whose parent or legal representative is willing to sign the Informed Consent Form (with photo release) and HIPAA Authorization.

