7.1.3 Skin Erythema and Skin Stripping

- Measured approximately 30 minutes after tape removal on Day 2 by an expert skin grader.

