7.2.4 Expert Skin Grader Assessments

At T0 (Baseline), Expert Skin Grader Assessments of Erythema will be made prior to the first tape application. At T24, Expert Skin Grader Assessments will be made approximately 30 minutes after the tape is removed. If the sample is missing at T24, no assessment will be conducted.

3M Confidential

Document Name: CLIN-PROT-ICH-US-05-327187

Clinical and Non-Clinical: CLIN-INDEX-3M-SPON-US-05-014050

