9.0 Statistics

9.1 Data Sets Analyzed

Data obtained for all subjects that enter the study and have samples applied will be analyzed in this study.

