13.4 Final Report

The investigator will provide a study report detailing the conduct of the study.

3M will have an analysis performed and prepare a final study report. The investigator will be provided with a copy of the report for his review and comment. The final report will be a record of the total study conduct and will be subject to review by the Investigator and 3M. The final report will assess and summarize all data collected and include:

- Sponsor and test material identification
- Study procedure
- Dates of study initiation and completion
- Copies of the raw data

Source data for this study will be maintained according to the study site's standard operating procedure.

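### No skin grade is taken at T24 when the tape has come off, although skin grades are safety analyses; separately, 9.4 leaves open what happens to data from dropped children

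*Combined protocol and SAP*

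**What the plan says.** **Skin grades.** Section 7.1.3 defines erythema and skin stripping as "Measured approximately 30 minutes after tape removal on Day 2 by an expert skin grader". Section 7.2.4 adds an exception: "If the sample is missing at T24, no assessment will be conducted". Section 7.2.1 gives a missing tape its own lift score (5), so the plan expects that this can happen. Section 7.2.3 does not retrieve fallen tapes. Section 9.2.2 names erythema, denudation and discomfort as the safety analyses, while 8.1 makes tape-related adverse events the principal safety measure.

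**Analysis set.** Section 9.1 reads: "Data obtained for all subjects that enter the study and have samples applied will be analyzed in this study". It sets no compliance condition. Section 9.4, which deals with missing and spurious data, reads: "Subjects who do not comply with the requirements of this study will be dropped". It then allows replacement so that at least 20 children complete, and provides for consultation if losses turn out to matter. It does not refer to 9.1. Section 13.4 says: "The final report will assess and summarize all data collected".

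**The concern.** The main point is the 7.2.4 exception. A child whose tape came off early was still exposed to the adhesive, and the skin is there to be looked at when the child returns. By instruction, nobody grades it. The erythema and denudation tables in 9.2.2 then describe only children whose tape stayed on, and the plan has no rule for reporting how many are missing or why.

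The second point is smaller. Section 9.4 does not say whether dropping a child ends participation only or also removes the data. It also leaves completion undefined, so 20 completers need not mean 20 FLACC results or 20 skin grades. The denominators of the FLACC comparison and of the skin tables are therefore not fully fixed in advance. That matters more than usual here, because the study has one arm and its results are set against those of a previous study.

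**Working it through.** No figure in the plan bears directly on either point, so there is none to reproduce. The sample size argument in 9.3 is not used here.

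**Step 1. What a tape-off child contributes.** Section 4.2 lists six endpoints.

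| Endpoint | As written | With a T24 skin grade |
|---|---|---|
| FLACC change | no; there is no removal to film (inferred from 7.2.2) | no |
| Hair count | no; tape not retrieved (7.2.3) | no |
| Skin cells (BCA) | no; tape not retrieved (7.2.3) | no |
| Erythema | no (7.2.4) | yes, listed |
| Denudation | no (7.2.4) | yes, listed |
| Lift | yes, score 5 (7.2.1) | yes |
| **Total** | **1 of 6** | **3 of 6** |

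Of the three variables named in 9.2.2, such a child supplies 0 of 3 at T24 as written, and 2 of 3 if the skin is graded.

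**Step 2. What else would record a reaction.**
- Section 8.2 leaves it to the investigator whether expected erythema or stripping is coded as an adverse event. Recording is mandatory only for a highly exacerbated reaction.
- Section 8.3 requires the CRF to state explicitly when a child had no adverse device effect, so each child gets a determination. Appendix 1 schedules this recording at T0 and T24.
- Section 7.2.5 calls for T24 photographs of skin reactions with no exception for missing tape, but 6.1.4 times them after tape removal.

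These sources cover the child's safety in part. None supplies a score on the erythema or denudation scale.

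**Step 3. How many children.** The documents give no tape-loss rate. Under assumed rates, the expected number without a skin grade among 20 children is:
- 5%: 20 × 0.05 = 1
- 10%: 20 × 0.10 = 2
- 20%: 20 × 0.20 = 4

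**Step 4. Sections 9.4 and 9.1 side by side.**
- If dropping ends participation only, 9.1 keeps whatever was obtained. A taped child dropped before T24 then has no FLACC result, T24 erythema grade or stripping grade to include.
- If dropping also removes data, the analysed set becomes compliers plus replacements.

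Section 2.6 caps enrolment at 24 with a target of 20, so the children who can depend on the reading number at most 24 − 20 = 4, or 4/24 = 16.7%. This is a ceiling, because 2.6 counts screening within the same 24.

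The rule can reach children who already wear the tape, since one requirement concerns the wear period: "Whose parent or legal representative agrees to not soak the tape during a sponge bath". The example is mild. It is an agreement made at entry, and the same criterion says what to do if the site gets wet.

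**The case against.** **On 7.2.4.** The endpoint is tied to a fixed interval after removal. Without a removal, that endpoint does not exist, and a grade taken after unknown wear and recovery is a different measurement. This stands, and it is why tape-off grades should be listed and not pooled. It does not justify leaving the skin ungraded, because a listed grade still makes a reaction visible. The plan also promises only descriptive summaries of the skin data, so there is no formal inference to protect.

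A reader might infer that a reaction in such a child would be recorded nowhere. The documents do not support that: the adverse device effect determination in 8.3 and the photographs in 7.2.5 narrow the gap.

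**On 9.4.** The section speaks of participation: withdrawing, being replaced, completing. Section 9.1 separately governs data obtained, and 13.4 points the same way. Read together, they favour keeping the data. This stands. A reader might infer that 9.4 contradicts 9.1 and makes the comparison compliers-only. That follows only on the less favoured reading, and no section states an exclusion from analysis.

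A conflict with 4.6.2 ("The Investigator may discontinue individual subjects from the study at any time") or 4.9.2 ("Protocol deviations are documented on a Protocol Deviation CRF") might also be inferred. Both are compatible with dropping a child, and 4.6.2 already requires the reason and date of discontinuation on the CRF.

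Finally, a reader might suspect selection on the primary outcome. FLACC is filmed only at T24, so dropping a child before then cannot select on an observed score.

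**Conclusion.** The skin-grade gap holds and is worth closing before the study starts. Followed exactly, 7.2.4 leaves a foreseen group of taped children without the T24 erythema and denudation grades that 9.2.2 treats as safety data. The effect is confined to the skin tables, since the principal safety measure in 8.1 still covers these children. How many children are affected rests on an assumed tape-loss rate.

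The 9.4 point holds as an ambiguity only. Its 16.7% ceiling requires that all 24 children be taped and that 4 of them be dropped for non-compliance. Nothing in the documents allows a statement about the size or direction of any bias, or about a false-positive rate.

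**What to change.** - **7.2.4:** grade erythema and stripping at the scheduled T24 visit whether or not the tape is present. List tape-off grades separately, with the reported time and reason for loss, and do not pool them with grades taken at the fixed interval in 7.1.3.
- **9.2:** report how many of all taped children have a FLACC result and how many have a skin grade, with reasons for those without.
- **9.4:** state that dropping ends participation only, that all data obtained from every taped child stay in the 9.1 set, that replacements are added and not substituted, and that any compliers-only analysis is a sensitivity analysis.

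The cost is a few sentences, one listing, and a grade by a grader already in place at a visit already planned. The downside is small: because wear and recovery times at tape-off sites are unknown, the added grades show reactions but do not complete the pooled tables.

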9.5 Deviations to Statistical Plan

Any deviation(s) from the original statistical plan should be described and justified in the final report, as appropriate.

10.0 Monitoring

3M, as sponsor of this study, is responsible for ensuring the proper conduct of the study with regard to protocol adherence and validity of the data recorded on the CRFs. 3M has therefore assigned a study monitor to this study. The progress of the study will be monitored by:

- Periodic on-site review
- Telephone communications
- Review of CRFs and source documents (e.g. Expert Skin Grader notes, photographs, video recordings, etc.)

The Investigator will give the 3M study monitor direct access to source documents that support data on the CRFs and make available such records to authorized 3M quality assurance, IRB, and regulatory personnel for inspection and/or copying.

Note: The Federal Privacy rule (HIPAA) specifically permits the use and disclosure of protected health information “to a person subject to the jurisdiction of the Food and Drug Administration (FDA) [e.g. study sponsor] with respect to an FDA-related product or activity for which that person has responsibility, for the purpose of activities related to the quality, safety, or effectiveness of such FDA-regulated product or activity” [45 CFR 164.512(b)(1)(iii)].

11.0 Quality Control and Quality Assurance

3M is responsible for implementing and maintaining quality assurance and quality control systems through written standard operating procedures (SOPs) to ensure that this study is conducted and data are generated, documented and reported in compliance with the protocol, GCP and regulations cited in Section 1.5 of this protocol. Study monitoring is carried out to accomplish this.

12.0 Ethics

This study will be conducted in accordance with the principles that have their origin in the Declaration of Helsinki, 21 CFR 50 (Informed Consent) and 56 (IRBs).

The study will start only after approval of the protocol and consent form by the IRB. The approval letter or notice must contain the IRB name and identification number, meeting date, and sufficient information to identify the protocol and informed consent by name and number that were reviewed. 3M, prior to study initiation, must receive a copy of the IRB approval letter.

12.1 Confidentiality

Participant confidentiality and privacy is strictly held in trust by the participating investigators, their staff, and the sponsor. This confidentiality is extended to cover testing of biological samples and genetic tests in addition to the clinical information relating to participants. Therefore, the study protocol, documentation, data, and all other information generated will be held in strict confidence. No information concerning the study or the data will be released to any unauthorized third party without prior written approval of the sponsor.

All research activities will be conducted in as private a setting as possible.

The study monitor, other authorized representatives of the sponsor, representatives of the Institutional Review Board (IRB), or regulatory agencies may inspect all documents and records required to be maintained by the investigator, including but not limited to, medical

3M Confidential

Document Name: CLIN-PROT-ICH-US-05-327187
Clinical and Non-Clinical: CLIN-INDEX-3M-SPON-US-05-014050

records (office, clinic, or hospital) and pharmacy records for the participants in this study. The clinical study site will permit access to such records.

The study participant's contact information will be securely stored at each clinical site for internal use during the study. At the end of the study, all records will continue to be kept in a secure location for as long a period as dictated by the reviewing IRB, Institutional policies, or sponsor requirements.

Study participant research data, which is for purposes of statistical analysis and scientific reporting, will be transmitted to and stored within 3M's secure electronic documentation system, based in St. Paul, MN. This will not include the participant's contact or identifying information. Rather, individual participants and their research data will be identified by a unique study identification number. The study data entry and study management systems used by clinical sites and by 3M's research staff will be secured and password protected.

13.0 Data Handling and Record Keeping

13.1 Study Personnel

Prior to study initiation, the Investigator must provide 3M with a signed Investigator Agreement (Statement of Investigator). The agreement contains pertinent investigator information (e.g. qualifications, experience, etc.) as well as the Investigator's commitment to conduct the study according to the protocol and all applicable state and federal regulations.

13.2 Pre-Study Documentation Requirements

Prior to study initiation, the Investigator must provide 3M with the following documents:

- Signed protocol including any amendments in place prior to study initiation
- Curriculum vitae for the Investigator and any co-investigators
- IRB-approved consent form
- HIPAA Authorization form
- IRB study approval letter
- IRB name, location and chairperson
- IRB membership list or identification number
- Signed investigator agreement (Statement of Investigator)
- Signed Research Agreement

13.3 Completion and Return of Case Report Forms

Paper case report forms (CRFs) will be provided by the study center for this study. Data may be recorded onto data collection sheets prior to entry on the CRFs, or it may be entered directly onto the CRFs. Once the forms are completed, the monitor will review the CRFs to ensure accuracy and completeness. The Investigator must review the CRFs for each subject in a timely fashion following completion.

13.4 Final Report

The investigator will provide a study report detailing the conduct of the study.

3M will have an analysis performed and prepare a final study report. The investigator will be provided with a copy of the report for his review and comment. The final report will be a record of the total study conduct and will be subject to review by the Investigator and 3M. The final report will assess and summarize all data collected and include:

- Sponsor and test material identification
- Study procedure
- Dates of study initiation and completion
- Copies of the raw data

Source data for this study will be maintained according to the study site's standard operating procedure.

13.5 Records, Reports and Retention Requirements

The Investigator will maintain study records for a minimum of 2 years following completion of the study. Records that must be maintained by the Investigator include, but are not restricted to:

- Signed study protocol, amendments, deviations
- IRB approval of study, protocol, and consent form
- Applications to the IRB
- Signed consent and authorization forms
- Case report forms
- Adverse event reports
- Correspondence relating to the study
- Sponsor Final Report

Appendix 1 Study Schedule

Study Day	-7 to -2	-1	T0	T24
Review Inclusion/Exclusion Criteria	x			
Obtain Consent and HIPAA Authorization (Parent/Legal Representative)	x			
Acclimate Subject to Study Staff and Facility	x			
Remind Parent/Legal Representative to Refrain from Applying Topical Medications, Creams, Powders, and Ointments on Test Site Area		x		
Confirm Inclusion/Exclusion Criteria			x	
Take Baseline Erythema Assessments			x	
Apply Test Material			x	
Assess Tape Lift				x
Record Video of Subject				x
Remove Test Material				x
Take Photos				x
Assess Erythema and Skin Stripping				x
Record Adverse Device Events			x	x
